6.3 Lifestyle Restrictions

6.3.1 Meals and Dietary Restrictions

Grapefruit and Seville oranges and their juices can inhibit CYP3A4 and should not be consumed while on study.

BMS-986242 should be administered following a light meal. However, the participant should avoid heavy meals with high fat content 4 hours prior to until 4 hours after BMS-986242 dose, except for participants in the substudy exploring food effect.

6.3.2 Caffeine, Alcohol, and Tobacco

Not applicable.

6.3.3 Activity

Not applicable.

6.4 Screen Failures

Screen failures are defined as participants who consent to participate in the clinical study but are not subsequently entered in the study/included in the analysis population. A minimal set of screen failure information is required to ensure transparent reporting of screen failure participants, to meet the Consolidated Standards of Reporting Trials publishing requirements, and to respond to queries from regulatory authorities. Minimal information includes date of consent, demography, screen failure details, eligibility criteria, and any serious AEs.

6.4.1 Retesting During Screening or Lead-in Period

This study permits the re-enrollment of a participant who has discontinued the study as a screen failure. If re-enrolled, the participant must be re-consented.

Retesting of laboratory parameters and/or other assessments within any single screening or lead-in period will be permitted (in addition to any parameters that require a confirmatory value).

The most current result prior to enrollment is the value by which study inclusion will be assessed, as it represents the participant's most current, clinical state.

Laboratory parameters and/or assessments that are included in [Table 2-1](#) may be repeated in an effort to find all possible well-qualified participants. Consultation with the Medical Monitor may be needed to identify whether repeat testing of any particular parameter is clinically relevant.

7 TREATMENT

Study treatment is defined as any investigational treatment(s), marketed product(s), placebo or medical device intended to be administered to a study participant according to the study randomization or treatment allocation.

Study treatment includes both Investigational [Medicinal] Product (IP/IMP) and Non-investigational [Medicinal] Product (Non-IP/Non-IMP) and can consist of the following:

An IP, also known as IMP in some regions, is defined a pharmaceutical form of an active substance or placebo being tested or used as a reference in a clinical study, including products already with

a marketing authorization but used or assembled (formulated or packaged) differently than the authorized form, or used for an unauthorized indication, or when used to gain further information about the authorized form.

Other medications used as support or escape medication for preventative, diagnostic, or therapeutic reasons, as components of the standard of care for a given diagnosis, may be considered as non-investigational products.

Both treatments used in this open-label study qualify as IPs, as per previous text, and their description and storage information are described in Table 7-1.

Product Description / Class and Dosage Form	Potency	IP/Non-IMP	Blinded or Open Label	Storage Conditions
BMS-986242-01 Film-coated Tablet	25 mg	IP	Open	Per label
BMS-986242-01 Film-coated Tablet	100 mg	IP	Open	Per label
Nivolumab Injection	10 mg/mL (100 mg/vial)	IP	Open	Per label

7.1 Treatments Administered

Participants will be assigned to a specific dose level as listed in [Section 5.1.2.1](#) in sequential order during dose escalation.

The selection and timing of dose for each participant are as follows (Table 7.1-1):

Study Treatment	Unit Dose Strength(s)/ Dosage Level(s)	Dosage Formulation Frequency of Administration	Route of Administration
BMS-986242	12.5-600 mg (dose levels 1-7)	QD	PO
Nivolumab	480 mg (flat dose)	Q4W	IV

Abbreviations: PO = per os, orally.

BMS-986242 (Part 1 and Part 2)

BMS-986242 should be administered in the morning following a light meal, approximately 24 hours apart. On the morning of Days 1 and 14, after an overnight fast of at least 10 hours, each participant will receive a single oral dose of BMS-986242 within, approximately, 5 minutes of completing a light meal. At the time of dosing, approximately 240 mL of water will be

administered to the participant along with BMS-986242. Serial PK samples will be collected on Days 1 and 14. The time of BMS-986242 administration will be called “0” hour. A description of a sample light breakfast meal is provided in Table 7.1-2.

Table 7.1-2: Representative Light Breakfast Meal

Food Item	Calories (kcal)	Fat (g)	Carbohydrates (g)	Protein (g)
2 slices of white bread	128	1.8	24.0	4.0
1 teaspoonful low-fat margarine	26	2.9	trace	trace
1 tablespoon jam	56	trace	13.8	trace
5 oz apple juice	71	0.2	17.5	0.2
5 oz skim (nonfat) milk	54	0.3	7.5	5.3
Total grams (g)	-	5.2	62.8	9.5
Total calories (kcal)	335	47	251	38
% of total calories	100	14	75	11

Source: US Department of Agriculture Nutrient Database for Standard Reference, Release 28 (September 2015)⁴⁸

Clinical Pharmacology Substudy

Fasting Treatment: Following an overnight fast of at least 10 hours, participants should be administered BMS-986242 with approximately 240 mL of water. No food should be allowed for at least 4 hours postdose. Water is allowed ad libitum except for 1 hour before and 1 hour after drug administration.

High-fat Meal Treatments: Following an overnight fast of at least 10 hours, participants will start the recommended meal 30 minutes prior to administration of BMS-986242. Study participants should eat this meal within 30 minutes or less; however, BMS-986242 should be administered 30 minutes after the start of the meal. BMS-986242 should be administered with approximately 240 mL of water. No food should be allowed for at least 4 hours postdose. Water is allowed ad libitum except for 1 hour before and 1 hour after drug administration.

A high-fat (approximately 50% of total caloric content of the meal) and high-calorie (approximately 800 to 1,000 calories) meal is recommended for the high-fat test meal treatment. This test meal should derive approximately 150, 250, and 500 to 600 calories from protein, carbohydrate, and fat, respectively. A description of a sample high-fat breakfast meal is provided in Table 7.1-3.

Table 7.1-3: Representative High-fat Breakfast

Food Item ^a	Calories (kcal)	Fat (g)	Carbohydrates (g)	Protein (g)
2 eggs fried	180	13.7	0.8	12.5

Table 7.1-3: Representative High-fat Breakfast

Food Item ^a	Calories (kcal)	Fat (g)	Carbohydrates (g)	Protein (g)
2 slices of white bread toasted	128	1.8	24.0	4.0
1 tablespoon butter	102	11.5	trace	0.1
2 strips of bacon fried	108	8.1	0.4	7.8
4 ounces of hash brown potatoes	207	9.8	27.4	2.3
8 fluid ounces (237 mL) of whole milk	149	8.0	11.7	7.7
Total grams (g)	-	52.9	64.3	34.4
Total calories (kcal)	874	477	257	138
% of total calories	100	55	29	16

^a Substitutions in this test meal can be made as long as the meal provides a similar amount of calories from protein, carbohydrate, and fat and has a comparable meal volume and viscosity.

Source: US Department of Agriculture Nutrient Database for Standard Reference, Release 28 (September 2015)⁴⁸

Restrictions related to food and fluid intake are described in [Section 6.3.1](#).

Nivolumab (Part 1 and Part 2)

During combination treatment, infusion of nivolumab should start approximately 30 minutes following BMS-986242. Nivolumab should be infused over 30 minutes. Further details regarding preparation and administration will be provided separately in site/pharmacy training materials.

Nivolumab will be administered IV as a flat dose. There will be no dose escalations or reductions of nivolumab allowed once assigned. There are no premedications recommended for nivolumab on the first cycle. If an acute infusion reaction is noted, participants should be managed according to [Section 7.7.1.5](#).

7.2 Method of Treatment Assignment

During the screening visit, the investigative site will call into the enrollment option of the IRT designated by BMS for assignment of a 5-digit participant number that will be unique across all sites. Enrolled participants, including those not dosed, will be assigned sequential participant numbers starting with 00001 (eg, 00001, 00002, 00003... 00010). The participant identification number will ultimately be composed of the site number and participant number. For example, the first participant screened (ie, enrolled) at site number 1 will have a participant identification number of 0001 00001. Once it is determined that the participant meets the eligibility criteria following the screening visit, the investigator site will call the IRT within 3 days prior to the first study treatment administration for the participant to be assigned to a treatment group.

During dose escalation, participants who are not evaluable for DLT determination may be replaced. Replacement participants will be assigned to the same treatment but will be assigned a new participant number.

7.3 Blinding

Not applicable.

7.4 Dosage Modification

7.4.1 Dose-limiting Toxicity

For the purpose of guiding dose escalation, DLTs will be defined based on the incidence and grade of AEs for which no alternate cause can be identified.

Part 1: Cycle 0 BMS-986242 (monotherapy lead-in) will have a 2-week DLT evaluation period (DLT1). The combination regimen will have 4-week DLT evaluation period (DLT2). Therefore, the total DLT assessment period is 6 weeks. Participants may proceed from Cycle 0 to Cycle 1 at each cohort unless any of the following events is observed: any DLT, Grade 2 or higher immune-related AEs considered related to BMS-986242 (eg, immune-mediated pneumonitis, colitis, hepatitis, nephritis, renal dysfunction) with the exception of immune-mediated hypothyroidism and hyperthyroidism, or Grade 2 AST and ALT elevation that does not resolve to Grade 1 within 1 week. For Grade 2 AST and ALT elevations that resolve to Grade 1 or baseline within 1 week, participants can be rechallenged with BMS-986242 monotherapy for a minimum of 5 days before proceeding to combination with nivolumab provided there is not a recurrence of Grade 2 event.

The total DLT period is 6 weeks, and participants must have received at least 75% of the BMS-986242 doses and 1 dose of nivolumab with observation for a minimum of 21 days following the first combination treatment dose to be considered evaluable for dose escalation decisions. Based on the predicted human half-life of BMS-986242 of 13 hours, this interval is expected to cover the anticipated timeframe for the occurrence of clinically significant immediate and early-onset AEs related to BMS-986242 monotherapy during Cycle 0 and repeat dosing of BMS-986242 in combination with nivolumab in Cycle 1.

The incidence of DLTs that occur within 6 weeks following the start of study treatment will guide dose escalation decisions. AEs will be graded according to the NCI CTCAE v4.03. For the purposes of participant management, study treatment-related AEs occurring at any time that meet the DLT definition will lead to dose interruption, dose modifications, and/or permanent discontinuation of study treatment as defined in [Section 8](#). Participants who withdraw from the study during the DLT evaluation interval for reasons other than a DLT may be replaced at the same dose level. The incidence of DLT(s) during the first cycle of treatment (the DLT evaluation period) will be used in dose escalation decisions and to define the MTD. AEs occurring after the DLT period will be considered for the purposes of defining the MTD, upon agreement between the Sponsor/Medical Monitor and investigators, if they are determined to have no clear alternative cause and are not related to disease progression.

For the purpose of guiding dose escalation, DLTs are defined below based on the incidence and grade of AEs for which no alternate cause can be identified.

Guidelines for management algorithms for immuno-oncology (I-O) agents and treatment of study treatment-related infusion reactions are provided in [Sections 7.7.1.4](#) and [7.7.1.5](#), respectively.

7.4.1.1 Dose-limiting Toxicities

Dose-limiting Toxicities for DLT1 and DLT2 Periods

Nonhematologic DLT:

A. Hepatic, Nonhematologic DLT

Any of the following events will be considered a hepatic DLT:

- Any \geq Grade 3 elevation of AST, ALT, or total bilirubin
- Grade 2 AST or ALT with symptomatic liver inflammation (eg, right upper quadrant tenderness, jaundice, pruritus)
- AST or ALT $> 3 \times$ ULN and concurrent total bilirubin $> 2 \times$ ULN without initial findings of cholestasis (elevated serum alkaline phosphatase; eg, findings consistent with Hy's law or Food and Drug Administration definition of potential drug-induced liver injury [DILI])*

*Note that this special category of DLT uses ULN rather than Common Toxicity Criteria Grade for definition.

B. Nonhepatic, Nonhematologic DLT

Any of the following events will be considered a nonhepatic, nonhematologic DLT:

- Grade 2 or greater episcleritis, uveitis, or iritis
- Any other Grade 2 eye pain or blurred vision that does not respond to topical therapy and does not improve to Grade 1 severity within 2 weeks OR requires systemic treatment
- Any Grade 3 or greater nondermatologic, nonhepatic, nonhematologic toxicity will be considered a DLT with the following specific EXCEPTIONS:
 - Grade 3 or Grade 4 electrolyte abnormalities that are not complicated by associated clinical adverse experiences, last less than 48 hours, and either resolve spontaneously or respond to conventional medical intervention
 - Grade 3 nausea, vomiting, or diarrhea that lasts less than 48 hours and either resolves spontaneously or responds to conventional medical intervention
 - Isolated Grade 3 elevation of amylase or lipase not associated with clinical or radiographic evidence of pancreatitis
 - Isolated Grade 3 fever not associated with hemodynamic compromise (eg, hypotension, clinical or laboratory evidence of impaired end-organ perfusion)
 - Grade 3 endocrinopathy that is well controlled by hormone replacement
 - Grade 3 tumor flare (defined as pain, irritation, or rash that localizes to site of known or suspected tumor)
 - Grade 3 fatigue
 - Grade 3 infusion reaction that returns to Grade 1 in less than 6 hours

C. Dermatologic DLT

- Grade 3 rash if no improvement (ie, resolution to \leq Grade 1) after a 1- to 2-week infusion delay. Participants who have not experienced a Grade 3 study treatment-related skin AE may resume treatment in the presence of Grade 2 skin toxicity.

- Grade 4 rash of any duration.

D. Hematologic DLT

- Grade 4 neutropenia \geq 5 days in duration
- Grade 4 thrombocytopenia or Grade 3 thrombocytopenia with bleeding or any requirement for platelet transfusion
- Grade \geq 3 febrile neutropenia for 48 hours
- Grade \geq 3 hemolysis (ie, requiring transfusion or medical intervention such as steroids)
- Grade 4 anemia not explained by underlying disease
-

• In addition to the above criteria, any toxicity that results in a participant not receiving at least 75% of the doses of BMS-986242 and the dose of nivolumab during the DLT evaluation period or causing greater than 2 weeks of dose delay will be classified as a DLT.

7.4.2 Guidelines for Dose Modification

Participants will be monitored continuously for AEs while on study treatment. Participants will be instructed to notify their physician immediately for any and all AEs. The criteria presented in this section and [Table 7.4.2-1](#) for dose modifications for BMS-986242 and delays are meant as general guidelines.

Participants will continue to receive study treatment as long as they have not had disease progression or study treatment-related AEs requiring dose modification as described below.

- Dose modification, interruption, or delay may occur in the setting of a lower-grade AE and/or be more conservative than indicated in [Table 7.4.2-1](#) based on the clinical judgment of the investigator and in consultation with the Sponsor/Medical Monitor.
- Dose reductions of BMS-986242 should be to the previous lower dose level.
- If several AEs of varying grades or severities occur simultaneously, the dose modification applied should be the greatest reduction applicable.
- Assessment of causality (chronology, confounding factors such as disease, concomitant medications, diagnostic tests, and previous experience with the agent) must be determined and documented by the investigator prior to dose modification.
- If the same AE recurs despite a dose reduction, a second dose reduction versus discontinuation of BMS-986242 will be discussed and agreed upon by the Sponsor/Medical Monitor and investigators.
- No more than 2 dose reductions of BMS-986242 will be allowed per participant. If a third dose reduction is required, the participant must discontinue BMS-986242. Dose re-escalation after a dose reduction may occur in limited circumstances (such as a change in attribution of an AE) after discussion and agreement of the Sponsor/Medical Monitor and investigators.
- Skipped doses will not be administered within the same cycle.
- For an AE requiring dose modification, BMS-986242 and nivolumab should be interrupted to allow recovery from the AE. Re-initiation of study treatment cannot occur until AE decreases to \leq Grade 1 or baseline assessment. In case of delayed recovery to \leq Grade 1 or baseline (except for alopecia) from treatment-related AEs that results in a delay of treatment for $>$ 6 weeks, the participant will not receive additional protocol-related treatment and will be removed from study unless discussed and agreed upon by the Sponsor/Medical Monitor and

investigators that it is in the best interest of the participant to receive additional treatment with BMS-986242 and nivolumab (eg, if the participant has demonstrated a response to treatment).

- During the DLT evaluation period, if a participant receives dose reduction and experiences a DLT at the lower dose, this DLT will be attributed to the highest dose level administered.
- For data collection and analysis purposes, all participants will continue to be classified by the original treatment arm.

Table 7.4.2-1: Dose Modifications

Dose Modification Criteria for Study Treatment-Related Adverse Events	BMS-986242 Monotherapy Modification at the Next Dose	BMS-986242 Combination Modification at the Next Dose
QTcF > 500 msec confirmed by at least 1 repeat ECG and at least 60 msec above baseline	Interrupt if needed to optimize electrolyte management. If event persists after electrolyte optimization (including dose modification of BMS-986242, if necessary), discontinue. Participants may proceed to get nivolumab monotherapy.	Interrupt if needed to optimize electrolyte management. If event persists after electrolyte optimization (including dose modification of BMS-986242, if necessary), discontinue. However, treatment with nivolumab may continue after discussion between PI and Medical Monitor.
Any other study treatment-related \geq Grade 3 adverse event that does not meet permanent discontinuation criteria (Section 8)	Decrease 1 level of BMS-986242 (no lower than 25 mg).	Decrease 1 level of BMS-986242 (no lower than 25 mg) in combination with same dose of nivolumab.
Grade 2 LFT abnormalities that do not resolve within 1 week	Interruption of BMS-986242 Continuation of BMS-986242 at a lower dose level may be considered after discussion with the Study Director/Medical Monitor. Participants may proceed to get nivolumab monotherapy.	NA
Grade 2 LFT abnormalities that resolve in 1 week	Interrupt dosing until improvement to Grade 1 or baseline and resume at same dose. If recurrence of Grade 2 LFT elevations, decrease 1 level.	NA

Abbreviations: LFT = liver function test; QTcF = QT interval corrected for heart rate using Fridericia’s formula; NA = not applicable; PI = principal investigator.

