5.1.3 Clinical/Safety Follow-up

Upon completion of study treatment, participants will enter the Clinical/Safety Follow-up period (refer to [Section 5.3](#) and Section 5.1.4 for definitions for end of treatment [EOT]).

Participants must be followed for at least 100 days after the last dose of study treatment. Follow-up visits should occur at Days 30, 60, and 100 (± 10 days) after the last dose of study treatment or should coincide with the date of discontinuation (± 10 days) if date of discontinuation is greater than 30 days after the last dose of study treatment to monitor for AEs. Participants will be required to complete 3 Clinical/Safety Follow-up visits regardless of whether they start a new anti-cancer therapy, except those participants who withdraw consent for study participation.

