7.4.4 Criteria to Resume Treatment

Participants experiencing AEs not meeting criteria for permanent discontinuation as outlined in [Section 8.1](#) and [Section 8.2](#) may resume treatment with study treatment under the following criteria:

- Participants may resume treatment with study treatment when the study treatment-related AE(s) resolves to Grade ≤ 1 or baseline value with the following EXCEPTIONS:
 - Participants may resume treatment in the presence of Grade 2 fatigue.
 - Participants who have not experienced a Grade 3 study treatment-related skin AE may resume treatment in the presence of Grade 2 skin toxicity.
- Participants with Grade 2 uveitis or eye pain or blurred vision not meeting DLT criteria ([Section 7.4.1](#)) must resolve to baseline prior to resuming study treatment.
- Study treatment-related pulmonary toxicity, diarrhea, or colitis must have resolved to baseline before treatment is resumed.
- Participants with study treatment-related endocrinopathies adequately controlled with only physiologic hormone replacement may resume treatment.
- If the criteria to resume treatment are met, the participant should restart treatment at the next scheduled time point per protocol.
- The consideration to re-initiate study treatment under these exceptions will be made on a case-by-case basis after considering the overall benefit/risk profile and in consultation between the investigator and the study Sponsor. Any AE with clinical risk will be assessed on a case-by-case basis with the investigator and the BMS Medical Monitor to determine the risks and benefits of continuing on study treatment following resolution versus discontinuing study treatment permanently.
- If treatment with study treatment is delayed > 6 weeks, the participant must be permanently discontinued from study treatment, except as specified in [Section 7.4.2](#).

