7.4.5 Guidelines for Permanent Discontinuation Secondary to Adverse Events

Participants will be required to permanently discontinue both study treatments for the following AEs:

- Clinical deterioration, as assessed by the investigator
- Grade 3 infusion reaction that does not return to Grade 1 in less than 6 hours
- Grade 3 pneumonitis, bronchospasm, neurologic toxicity, uveitis, or myocarditis
- Life-threatening skin toxicity (toxic epidermal necrolysis)

- Any Grade 4 AE; however, an exception may be made for the following upon consultation between the investigator and BMS Medical Monitor:
 - Grade 4 electrolyte abnormalities < 72 hours in duration
 - Grade 4 neutropenia < 7 days in duration
 - Grade 4 lymphopenia
 - Grade 4 increase in amylase or lipase that is not associated with clinical or radiographic evidence of pancreatitis
- Abnormal liver function tests meeting criteria for a potential DILI.
- Any dosing delay lasting > 6 weeks will be cause for permanent discontinuation. Extensions to the period of dose delays may be granted for individual participants on a case-by-case basis after specific consultation and agreement between the investigator and BMS Medical Monitor in settings where benefit/risk may justify continued study treatment (eg, participant deriving clinical benefit who requires prolonged steroid taper for management of non-DLT immune-related AEs or experiences delays for management of a non-treatment-related AE).
- Accordingly, dosing delays to allow for prolonged steroid tapers to manage study treatment-related AEs are allowed. Additionally, dosing delays > 6 weeks that occur for non-treatment-related reasons may be allowed if approved by the BMS Medical Monitor.
- The consideration to re-initiate study treatment under these exceptions will be made on a case-by-case basis after considering the overall benefit/risk profile and in consultation between the investigator and the Sponsor.
- Prior to re-initiating treatment in a participant with a dosing delay lasting > 6 weeks, the BMS Medical Monitor must be consulted.
- Tumor assessments should continue per protocol even if dosing is delayed.

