All participants who discontinue the IP should comply with protocol-specified follow-up procedures as outlined in [Section 8.2](#). The only exception to this requirement is when a participant withdraws consent for all study procedures, including post-treatment study follow-up, or loses the ability to consent freely (eg, is imprisoned or involuntarily incarcerated for the treatment of either a psychiatric or physical illness).

If study treatment is discontinued prior to the participant's completion of the study, the reason for the discontinuation must be documented in the participant's medical records and entered on the appropriate case report form (CRF) page.

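### Section 7.4.2 takes participants out of the study after a treatment-related delay of more than 6 weeks, while the rest of the protocol stops only their treatment: very likely a slip, to be reworded

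*Combined protocol and SAP*

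**What the plan says.** **The rule in question.** Under Section 7.4.2, an AE that requires dose modification interrupts both drugs, and treatment restarts only once the AE is back to Grade 1 or baseline. If slow recovery from a treatment-related AE delays treatment by more than 6 weeks, the section says "the participant will not receive additional protocol-related treatment and will be removed from study unless discussed and agreed upon by the Sponsor/Medical Monitor". Investigators must also agree, and the agreement must be that further treatment serves the participant best. The section also says that its criteria for dose modifications and delays "are meant as general guidelines".

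**The same 6-week limit elsewhere.** In Section 7.4.4, after a delay of more than 6 weeks "the participant must be permanently discontinued from study treatment, except as specified in" Section 7.4.2. Section 7.4.5 lists the limit among the reasons to stop both study treatments for good: "Any dosing delay lasting > 6 weeks will be cause for permanent discontinuation". It allows extensions agreed with the Medical Monitor and delays for prolonged steroid tapers.

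**Follow-up after treatment stops.**
- Section 7.4.5: "All participants who discontinue the IP should comply with protocol-specified follow-up procedures as outlined in" Section 8.2. It continues: "The only exception to this requirement is when a participant withdraws consent for all study procedures, including post-treatment study follow-up". The same sentence then adds loss of the capacity for free consent.
- Section 5.1.3: "Participants must be followed for at least 100 days after the last dose of study treatment". Visits fall at Days 30, 60 and 100, and only withdrawal of consent exempts a participant.
- Section 5.1.4: every participant goes on to survival follow-up until 2 years after the last dose. Those with stable disease, partial response or complete response (SD, PR or CR) at the end-of-treatment (EOT) visit also have response follow-up.
- Section 8.1.1: those who stop treatment are followed until death or the end of the study.

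**The concern.** Section 7.4.2 names two consequences and joins them: no more protocol treatment, and removal from the study. If the second meant only that treatment stops, it would repeat the first. The one exception is an agreement to give more treatment, and nothing in the sentence preserves follow-up for a participant who is not given more. On the words alone, that participant leaves the study. Under Sections 5.1.3, 5.1.4, 7.4.5 and 8.1.1 the same participant must be followed.

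The participants concerned are those slow to recover from treatment-related toxicity on a compound with no prior human use (Section 3.3.1). AEs and deaths are primary endpoints (Section 4). A site that applied the sentence literally would stop scheduled safety visits and laboratory tests for these participants, and would cut short their follow-up for progression, response duration and survival.

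**Working it through.** The plan states no figure on this point. The check is a comparison of texts, followed by date arithmetic for the literal reading.

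**1. Do the rules conflict?**

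| Section | Trigger | Consequence | Exception |
|---|---|---|---|
| 7.4.2 | Slow recovery from a treatment-related AE, delay > 6 weeks | No more treatment, and out of the study | Agreement to treat further |
| 7.4.4 | Delay > 6 weeks | Study treatment stops | As in 7.4.2 |
| 7.4.5 | Any delay > 6 weeks | Both treatments stop; follow-up continues | For stopping: agreed extension, steroid taper. For follow-up: consent withdrawn or ability to consent lost |
| 5.1.3 | Treatment ended | 100 days, 3 visits | Consent withdrawn |
| 5.1.4 | Safety follow-up completed | Survival follow-up for all | None stated for toxicity |
| 8.1.1 | Treatment stopped | Followed until death or study end | None stated for toxicity |

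Only Section 7.4.2 ends participation, and no follow-up section exempts a toxicity delay. The conflict with 5.1.3, 5.1.4, 7.4.5 and 8.1.1 is direct. Section 7.4.4 differs in its consequence but refers back to 7.4.2, so it is not a flat contradiction.

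**2. Which reading is more likely?** Section 7.4.4 treats 7.4.2 as the source of an exception to a treatment-stopping rule. Section 5.1.4 speaks loosely of discontinuing the study for participants who then enter response follow-up, where it can only mean stopping treatment. Both point to a slip.

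**3. What would the literal reading end, per affected participant?** Assumption: Day 0 is the last daily dose of BMS-986242 and the delay runs from it, since Section 7.4.2 interrupts both drugs together.

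- Earliest removal: 6 × 7 = Day 42.
- Day 30 visit: not counted as lost. Section 5.1.3 lets a visit coincide with the discontinuation date "if date of discontinuation is greater than 30 days after the last dose of study treatment to monitor for AEs", and 42 > 30.
- Day 60 visit: its window opens at 60 − 10 = Day 50, after Day 42, so it is lost. So is Day 100. That is 2 of 3 visits.
- Safety period lost: 100 − 42 = 58 of 100 days.
- Survival period: it follows the safety period, so from Day 100 to Day 730 it is 730 − 100 = 630 days, all lost. Counting from removal gives 730 − 42 = 688 days, but 58 of those are the safety days above and should not be counted twice.
- Response imaging: lost for those with SD, PR or CR. No scan count is given, because Table 2-3 places the EOT visit in two ways (footnotes a and c), and response follow-up starts only after the safety period, whose Day 100 visit has its own tumor assessment.

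A later removal date would require BMS-986242 to have stopped well before the delay clock started, for instance in someone already on nivolumab alone. That is a special case and is not used here.

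**4. What would survive removal?** Section 9.2.1 requires serious AEs to be collected until 100 days after nivolumab stops and does not tie this to visits. Appendix 3 counts death as a serious AE. Sections 9.2 and 9.2.3 keep known related AEs under follow-up. Collection of nonserious AEs is less secure, because Section 9.2.1 sets it at the Schedule of Activities time points.

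**The case against.** The strongest reply is that no careful site would act on the phrase. Section 7.4.2 describes its own criteria as guidelines. Section 9 makes adherence to the Schedule of Activities mandatory and rules out waivers, and Table 2-4 assigns survival follow-up to all participants. Section 7.4.1 lists interruption, modification or permanent discontinuation of treatment as the consequences of a dose-limiting toxicity, and does not list leaving the study. Section 8.2, which governs leaving the study, gives no toxicity ground. Section 7.4.5 narrows the group further through its steroid-taper and extension provisions.

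Most of this stands, and it is why the point is minor. It does not remove the conflict. The sentence is worded as an instruction, no clause gives another section precedence, and the explicit promise in Section 8.2 to keep people in the study covers those who ask to stop treatment, which a participant stopped under the 6-week rule has not done.

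A reader might go further and infer that serious AEs and early deaths would be missed, because Section 9.2.1 does not oblige investigators to seek events in former participants. The documents do not support that. The statement concerns people already discharged from the study, and the 100-day duty stands in the same section.

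**Conclusion.** Section 7.4.2 is wrong as written and should be corrected, as a minor wording correction to an operative rule. It contradicts Sections 5.1.3, 5.1.4, 7.4.5 and 8.1.1 and departs from Section 7.4.4, very probably because a word was dropped.

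The loss is zero if sites follow the other sections, to which most of the protocol points. On a literal reading, and with the delay counted from the last daily dose, each affected participant would lose the Day 60 and Day 100 safety visits, all survival contacts to 2 years, and response imaging where it applies.

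A reader might infer biased estimates of late toxicity, progression-free survival or overall survival from toxicity-related dropout. The documents do not support that claim: they give no rate of delays beyond 6 weeks, and Section 10.3.1 leaves censoring to a statistical analysis plan still to be written. Nor do they support the view that the sponsor meant to end follow-up. No design figure changes.

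**What to change.** In Section 7.4.2, replace the removal phrase so that the participant *will be permanently discontinued from study treatment, will remain in the study, and will be followed per Sections 5.1.3, 5.1.4 and 8.1.1*. Leave the 6-week limit and its exception as they are.

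The cost is one phrase in the next amendment. The visits, survival contacts and scans are already scheduled in Sections 5.1.3 and 5.1.4 and in Table 2-4, so no procedure is added.
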